The overall objective of this multicenter trial is to determine whether use of a low-cost, high-resolution microendoscope during diagnostic upper endoscopy can improve the efficiency and accuracy of endoscopic screening for esophageal squamous cell neoplasia (ESCN). This is a trial of a novel technology, a miniaturized, low cost (<\$3,500) microscope device which can be used during upper endoscopy to image the gastrointestinal epithelium. This portable, battery-operated high-resolution microendoscope (HRME) was developed by our collaborators at Rice University and provides greater than 1000X magnified images of the esophageal mucosa. In a single-arm, pilot study of the device in an enriched population of 60 high-risk subjects in China and the US, we used the microendoscope during routine Lugol's chromoendoscopic screening to categorize areas of abnormality (unstained areas). The sensitivity /specificity for the device seen in this study were 100% and 79%-a significant improvement over the sensitivity/specificity of Lugol's chromoendoscopy which were 97% and 52%. Thus, our presumption is that HRME can enhance the specificity (and lower the false positive rate) of Lugol's. As part of a National Cancer Institute R01 supplement (Figure 1), we have enhanced the current HRME technology by introducing an automated, ergonomic, augmented reality platform. The augmented reality platform displays, in real-time, the microscopic image colocalized with the endoscopic image, potentially allowing more targeted biopsies/treatment and increased accuracy. Our central hypothesis is that our approach can improve the efficiency and clinical impact of endoscopic screening and surveillance of ESCN by providing *in-vivo* optical biopsies comparable to standard histology. Specifically, HRME will facilitate accurate, rapid real-time endoscopic screening by non-expert clinicians. We also hypothesize the HRME will provide additional, more accurate information regarding the presence of neoplasia that will impact upon the physician's decision to obtain a mucosal biopsy or perform endoscopic therapy (endoscopic mucosal resection or ablation). This could potentially minimize the number of unnecessary biopsies and enable the physician to perform endoscopic therapy at the time of the initial examination, rather than delaying endoscopic treatment to another procedure following pathologic confirmation of the initial biopsies. We will compare (1) the current endoscopic "standard of care" (white light endoscopy with Lugol's iodine), (2) HRME with subjective, human interpretation, and (3) augmented reality HRME (software, 'machine' interpretation). The addition of (3) is the basis for our revision R01 and this amended IRB. The accuracy, efficiency, clinical impact and cost-effectiveness of each approach in the diagnosis and management of ESCN will be determined in both the Chinese and US healthcare systems. Specific endpoints: 1. Efficiency: (a) Diagnostic Yield: The number of neoplastic biopsies/total number of biopsies obtained in patients who receive biopsies. (b) 'Patients saved': Number of patients who receive no biopsies (c) Procedure time: Total procedure time in each group 2. Clinical impact: Determine potential clinical impact of HRME by determining if use of the device (with both subjective and automated read) changes the decision to perform endoscopic therapy and perform, or not perform, a mucosal biopsy when compared to LC alone. 3. Prospectively compare the performance characteristics of HRME-LC to LC for the prediction of squamous esophageal neoplasia in flat mucosa and mucosal lesions using histopathology as the gold standard. (a) Determine the sensitivity, specificity, positive and negative predictive value for the identification of neoplasia on a per biopsy and per patient analysis. 4. Determine the cost-effectiveness of HRME-LC to LC alone for the endoscopic screening and surveillance of ESCN in the US and China.

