All-inclusive outpatients undergoing routine (standard of care) Lugol's chromoendoscopic evaluation for suspected or known squamous cell neoplasia will be enrolled as well as any outpatients referred to the clinic with any prior history of squamous cell dysplasia and/or neoplasia will also be considered eligible as they will serve as study population for the surveillance group. Patients seen in outpatient clinics who are high risk for esophageal dysplasia/neoplasia, including patients with known history of head/neck cancer or of Northern Chinese descent will also be eligible for enrollment.

Six novice and four expert endoscopists will be the research subjects for the post hoc image analysis project. The subjects will be practicing endoscopists or GI fellows at current study sites or other institutions.

Exclusion Criteria:

- Allergy or prior reaction to the fluorescent contrast agent proflavine - Patients who are unable to give informed consent - known advanced squamous cell carcinoma of the distal esophagus, or dysplastic/suspected malignant esophageal lesion greater than or equal to 2cm in size not amenable to endoscopic therapy - Patient unable to undergo routine endoscopy with biopsy: - women who are pregnant or breastfeeding - prothrombin time greater than 50% of control; PTT greater than 50 sec, or INR greater than 2.0 - inability to tolerate sedated upper endoscopy due to cardio-pulmonary instability or other significant medical issues

F2. Procedure

Written informed consent will be obtained prior to study participation using the IRB-approved consent form.

The patient will be assigned to one of two groups: Group A: HRME-LC (HRME + Lugol's) or Group B (Lugol's alone). Randomization assignments (HRME-LC vs. LC) will be computer-generated with allocation concealment using sealed envelopes. As part of the NCI R01 supplement, the HRME-LC arm will now include the augmented reality HRME component following the standard HRME image. The Augmented Reality (AR) glasses will allow the endoscopist to see the microendoscopic (HRME) and endoscopic image at the same time. We now can produce a colocalized image that can be seen on the glasses at the same time as the endoscopic image AND in the same field of view. This does NOT change patient care. Rather, it improves the visualization of the endoscopist as shown in Figure 1.

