In both groups, per standard of care, endoscopic examination will be performed using white-light endoscopy with Lugol's dye-spray. In each subject, the location of each unstained area (level, quadrant) will be recorded and digital images obtained. The endoscopist's clinical impression will be recorded for each Lugol's abnormal area and visible lesion ('nonneoplastic' vs. 'neoplastic') as well as his/her proposed plan: a. no biopsy, b. biopsy, c. endoscopic treatment/removal. In the standard-of-care arm (Group B), biopsies will be obtained of all Lugol's abnormal areas. Likewise, Group A will receive the clinician subjective HRME read + augmented reality software HRME read, sequentially, of all Lugol's unstained (abnormal) areas prior to tissue biopsy. For imaging, 1-10 ml proflavine hemisulfate (0.01%) will be sprayed on the esophageal mucosa. The HRME probe placed gently on the mucosa and the augmented reality microscopic (HRME) image displayed on the glasses, with the endoscopic image (monitor) behind it. The endoscopist will first make a subjective interpretation (neoplasia vs. no neoplasia) and plan of action (biopsy, no biopsy, treat) WITHOUT the image-analysis software. Once this qualitative ("Human") read is recorded, the image analysis software will be turned on and the software diagnosis provided in real-time. This quantitative ("Machine") read and the revised plan of action will be recorded. The HRME procedure (including Human and Machine reads) as well as standard endoscopy and biopsy time will be recorded. The research coordinators will indicate the biopsy number/location on an esophageal map diagram. The biopsies from each site will be placed in formalin per standard of care and labeled according to biopsy location (quadrant: 12, 3, 6, 9 o'clock). In all subjects, all Lugol's abnormal areas will be biopsied (to uphold the standard of care, per IRB); however, HRME "non-neoplastic" sites will be considered not tissue-biopsied for purpose of the analysis. All biopsies will be submitted for consensus diagnosis by 2 expert GI pathologists.

A schematic of the existing trial with the proposed revision is shown in Figure 2. The IRB revision is shown in RED. We anticipate that this revision will add an additional 30-60 seconds per procedure but will otherwise not change patient care.

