Separately, 10 endoscopists (6 novice and 4 expert) will be asked to interpret a selection of the HRME images. The novices will include current GI fellows at BCM and novice endoscopists on the protocol, while the expert endoscopists will be experienced endoscopists listed on the protocol. The 10 subjects will receive information about the procedures verbally as a waiver of documentation of consent is requested. Each of the subjects will first receive training using a training set, and then will be evaluated using a testing set of images. They will be asked to give a read (neoplastic or non-neoplastic) and then to provide their confidence level (high or low) for each image determination. Following the subjective HRME image read, each image will be evaluated using the automated software algorithm, with the subjective and automated reads being blinded to each other, as well as to the gold standard consensus pathology read by 2 expert GI pathologists. The subjective reads will be compared to the automated reads and the consensus pathology reads.

Subjects at the Jilin site will be asked to complete a survey addressing barriers to esophageal cancer screenings. Subjects will be asked about beliefs and attitudes surrounding screening techniques.

Section G: Sample Size/Data Analysis

G1. Sample Size

How many subjects (or specimens, or charts) will be used in this study?

Local: 300 Worldwide: 1300

Please indicate why you chose the sample size proposed:

This is an IRB revision and will NOT change our proposed sample size. Rather, in the remaining patients to be accrued, we will determine the accuracy of our revised (AR platform). Thus, the goals and sample size of the original trial will remain intact which is to compare LCE to LCE+HRME (subjective read).

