Sample Size Calculation (This has NOT changed from original IRB): The sample sizes are calculated separately for the two risk groups (650 in surveillance group and 650 in screening group). Among the surveillance group, we want to test non-inferiority in sensitivity and superiority in specificity of LCE+HRME vs. LCE alone. The standard endoscopic evaluation using LCE has high sensitivity of about 95% but with low specificity at about 65%. Based on the preliminary data, we hypothesize that LCE+HRME has the sensitivity of at least 90% level, which is similar to that of LCE, but LCE+HRME would improve the specificity to 85%. With significance level of 0.05 and 80% power, we need 223 neoplastic patients and 65 benign patients in each arm (LCE and LCE+HRME) to conclude that LCE+HRME has similar sensitivity as LCE alone and had higher specificity than LCE alone. Hence, we need 446 neoplastic patients and 130 benign patients. The sample size calculation is based on the formula in Pepe (Chapter 8, The statistical Evaluation of Medical Tests for Classification and Prediction, 2003).

According to the preliminary results, greater than 80% patients in the surveillance group would have neoplasia. We anticipate the enrollment of total 650 patients in the surveillance group to ensure the accrual of 446 neoplastic patients and 130 benign patients.

In screening group, we will study the accuracy of LCE+HRME for the diagnosis of neoplasia, and test whether the negative predictive value (NPV) of LCE+HRME is higher than LCE alone. The NPV for using LCE alone is about 95%. We hypothesize that the NPV for LCE+HRME should be at least 99% to be useful. A sample of 300 per arm would provide 82.1% power for this hypothesis with a 5% type-I error. Assuming an 8% loss to follow-up or incomplete data, we need to recruit 325 subjects per arm in the screening population.

Power Calculation (Augmented Reality HRME Revision): We anticipate having at least 400-500 subjects remaining by the time the Augmented Reality HRME revision IRB is approved and funding from the NCI obtained. With 400 patient Augmented Reality HRME data, assuming an accuracy of 83% AND 650 LC patient, assuming an accuracy of 57%, the study should have >93% power to detect a statistically significant difference with an alpha error rate of 0.05.

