Diagnostic yield: This is defined as the proportion of all biopsies that are truly neoplastic over the total number of biopsies obtained in patients who receive biopsies. A generalized linear model for logistic regression with multiple correlated binary outcomes within each patient will be used for data analysis. In this model the binary outcome for each biopsy specimen is whether the specimen is neoplastic or non-neoplastic, and the explanatory variable is the arm (LCE+HRME vs. LCE alone) stratified by group (screening and surveillance). PROC GLIMMIX in SAS will be used because of the correlations among samples from the same patient. The model will allow for testing whether the proportion of samples classified as neoplasia differs between the 2 arms.

'Clinical efficiency': For patients that have benign disease confirmed by histology, the true proportion of patients potentially saved any biopsy using HRME (Lugol's + and HRME -) will be estimated by 95% confidence intervals (stratified by group). Proportions will be compared between groups by the chi-square test or Fisher's exact test. Procedure time in the HRME+LC arm will be compared to the LC arm by analysis of variance, stratified by group (screening and surveillance). An interaction term will also be included to determine to what extent the difference in procedure time between the 2 arms varies between the 2 risk groups.

Clinical impact: For this, the proportion of patients who had a change in the decision to perform endoscopic therapy or mucosal biopsies as a result of LCE+HRME or LCE alone, will be estimated by a 95% confidence interval. This proportion will be compared between LCE+HRME and LCE alone by the chi-square test or Fisher's exact test.

Progression rates: Five year follow-up of progression rates to more advanced pathology or esophageal cancer (EC) in the 2 arms will be conducted. Progression rates and their 95% confidence interval will be summarized and compared between LCE+HRME and LCE alone by the chi-square test or Fisher's exact test.

Safety/Adverse Events: Immediate and 48 hour adverse event (AE) rates will be compared between the LCE+HRME arm and LCE alone arm by the chi-square test or Fisher's exact test. The AE rates and their 95% confidence intervals will be summarized.

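### The clinical-impact analysis does not say which recorded plan counts as the HRME decision, although the software read exists only for HRME patients enrolled after the augmented-reality revision

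*Combined protocol and SAP*

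**What the plan says.** - **Section D (Purpose and Objectives).** Three approaches are to be compared: Lugol's chromoendoscopy (LCE), HRME read by the endoscopist, and augmented-reality (AR) HRME read by software. "The accuracy, efficiency, clinical impact and cost-effectiveness of each approach in the diagnosis and management of ESCN will be determined" in both health systems. Endpoint 2 asks "if use of the device (with both subjective and automated read) changes the decision to perform endoscopic therapy" or the decision to biopsy, relative to LCE alone.
- **F2 (Procedure).** The software read is a mid-trial addition: "the HRME-LC arm will now include the augmented reality HRME component following the standard HRME image". Under the current procedure the HRME arm yields three plans in sequence. One is recorded after Lugol's (in both arms), one after the endoscopist's subjective read with the software off, and one after the software is turned on, when the machine "read and the revised plan of action will be recorded". The LCE-alone arm has only the first of these.
- **G1 (Sample Size).** The goals and size of the original trial are unchanged, and its comparison of LCE with LCE+HRME is tied to the subjective read. For the revision, "in the remaining patients to be accrued, we will determine the accuracy of our revised (AR platform"). On numbers: "We anticipate having at least 400-500 subjects remaining" when the revision is approved and funded. The power sentence that follows uses 400 AR-HRME patients against 650 LCE patients, for accuracy.
- **G2 (Data Analysis, Clinical impact).** The plan estimates, with a 95% confidence interval, "the proportion of patients who had a change in the decision to perform endoscopic therapy or mucosal biopsies as a result of LCE+HRME", does the same for the control arm, and compares the arms by a chi-square or Fisher's exact test. It names no read, no recorded plan and no enrolment period.

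**The concern.** For an HRME patient enrolled after the revision, a change in decision could mean three things: the plan after the human read differs from the plan after Lugol's, the final software-informed plan differs from it, or either step brought a change. G2 does not choose, so two analysts could report different results from the same data.

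Under the second or third rule, post-revision patients are scored on a human-plus-software decision and pre-revision patients on a human-only decision. Running the software later on stored images would not repair this, because it cannot show what the endoscopist would have decided.

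Clinical impact is a named endpoint and part of the central hypothesis. The natural question for the revision is whether the software changes decisions beyond the human read. F2 records the two plans needed, in order, in the same patient, but no analysis in G2 uses that pairing.

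**Working it through.** **1. The denominator.** The plan's total of 1300 (G1) can be rebuilt.
- Surveillance: 130 benign patients at 80% neoplasia need 130 / (1 - 0.80) = 650, which gives 650 x 0.80 = 520 neoplastic patients, above the 446 required.
- Screening: 300 / (1 - 0.08) = 326.1, so 327 per arm against the stated 325, a difference of 2.
- Total: 650 + 2 x 325 = 1300. At 1:1 this is 650 per arm, which agrees with the 650 LCE patients in the AR power statement.

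G1 gives no sample size or power for clinical impact itself.

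**2. HRME patients without a software read.** Share = (650 - post-revision HRME patients) / 650.

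| Reading of the 400-500 remaining | With software read | Without | Share without |
|---|---|---|---|
| Both arms, 1:1 (assumed) | 200-250 | 400-450 | 62-69% |
| All in the HRME arm, as the power statement's 400 implies | 400-500 | 150-250 | 23-38% |

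The plan says at least 400-500, so the shares without a software read could be lower.

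**3. What pooling does.** Let h be the change proportion scored on the human-read plan. Let d be the difference made by scoring post-revision patients on the final plan, or on any change. Let f be the share of the arm enrolled after the revision. If h is the same in both periods, the pooled proportion is h + f x d.
- Both-arms reading: f = 200/650 to 250/650 = 0.308 to 0.385.
- HRME-arm reading: f = 400/650 to 500/650 = 0.615 to 0.769.

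Each 10 points of d therefore move the pooled value by 3.1-3.8 or 6.2-7.7 points. With assumed rates that are not in the documents (h = 20%, d = +10 points), the pooled value is 23.1-23.8% or 26.2-27.7%. That is neither the human-read figure (20%) nor the human-plus-software figure (30%).

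The sign of d depends on the rule. Under any-change scoring it cannot be negative. Under final-plan scoring the software may reverse a human-read change, and d may be negative.

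**4. Precision if the reads are separated.** The 95% half-width is 1.96 x sqrt(p(1-p)/n), at its widest for p = 0.5.
- Human read, n = 650: +/-3.8 points.
- Software read, n = 200-250: +/-6.9 to +/-6.2 points.
- Software read, n = 400-500: +/-4.9 to +/-4.4 points.

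**The case against.** The strongest reply is that no composite was intended. Section D lists the human and software reads as separate approaches and promises the clinical impact of each, so its mention of both reads can mean each in turn. G1 ties the LCE+HRME label to the subjective read and confines the AR evaluation to patients still to be accrued. This is a fair reading, and no section combines the two reads into one score. It does not close the gap. G1 speaks of accuracy and the original goals, not of clinical impact. If each read is meant in turn, G2 needs two analyses, with the software one limited to post-revision patients, and it gives one.

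Three stronger inferences are tempting, and the documents do not support them.
- *The endpoint cannot be scored.* F2 records the human-read plan before the software is on, so that component needs no software read. Only the automated component is missing before the revision.
- *Most of the HRME arm is affected.* This is true on one reading of the 400-500 and false on the other.
- *The pooled figure is inflated, because later patients have two chances to change.* That presumes an any-change rule found nowhere in the plan.

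Two cautions also stand. F2 describes the current procedure, and the documents do not show which plans the pre-revision forms captured. F2 also has the HRME image shown on the glasses before the subjective read, so the human read itself may have been made under a different display after the revision.

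**Conclusion.** The concern holds as a gap in the specification of one secondary analysis. G2 does not say which recorded plan defines the HRME decision, and it does not restrict the software-informed decision to the patients who have one. Between 23% and 69% of the HRME arm lacks that decision, depending on whether the 400-500 remaining subjects are an HRME-arm count or a total split 1:1. If the final plan or any change were scored, the result would mix two exposures and depend on when the revision started. By how much, and in which direction, cannot be derived from the documents; the percentages in step 3 only illustrate the mechanism. If the human-read plan is scored, the mixture of reads does not arise, provided the plans were recorded from the start.

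A related gap remains under any scoring rule. The LCE-alone arm has one recorded plan, so the change in decision that G2 compares between arms is undefined for that arm.

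**What to change.** In G2, Clinical impact:
- **(a)** For all HRME-arm patients, report the within-patient change from the post-Lugol's plan to the plan recorded after the human read and before the software is on, with a 95% confidence interval. Confirm that the pre-revision forms captured both plans. Tabulating the result by enrolment period as well would show any effect of the new display.
- **(b)** For post-revision HRME patients only, report separately the within-patient change from the human-read plan to the software-revised plan, with a 95% confidence interval. Any between-arm comparison involving the software read should use concurrently randomised LCE patients.
- **(c)** Align endpoint 2 in Section D with (a) and (b), and state in G1 whether 400-500 is a total or an HRME-arm count.
- **(d)** Redefine the chi-square or Fisher comparison with LCE alone, for example as a comparison of the recorded plans between arms.

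The cost is SAP wording and one more table. No new data are needed if the pre-revision forms recorded the plans. The drawback is that the software-read estimate rests on the smaller post-revision set, with the wider intervals shown above.

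### The prothrombin-time exclusion is unusable as written: read literally it bars patients with normal clotting, so sites must substitute a rule of their own

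*Combined protocol and SAP*

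**What the plan says.** Section F1 (Design), under Exclusion Criteria, gives one line on clotting: "prothrombin time greater than 50% of control; PTT greater than 50 sec, or INR greater than 2.0". It contains three limits, and the natural reading is that meeting any one of them excludes the patient. Nothing else in the document defines control, restates the limit, or says that the percentage is an increase over control.

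The inclusion criteria in the same section describe a routine outpatient population: "All-inclusive outpatients undergoing routine (standard of care) Lugol's chromoendoscopic evaluation for suspected or known squamous cell neoplasia will be enrolled". Section F2 (Procedure) shows why a clotting limit is needed: "In all subjects, all Lugol's abnormal areas will be biopsied". Section H3 says that the protocol will be translated into Chinese for the two collaborating hospitals in China.

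**The concern.** The line sets two limits on closely related measures of clotting, since the INR is a standardised form of the prothrombin time. The two should point the same way, but as worded the prothrombin limit falls below the normal value while the INR limit lies well above it. A patient with entirely normal clotting is excluded by one and untouched by the other.

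What is at stake is consistent eligibility. The criterion guards against bleeding in patients who may be biopsied, and Section E1 classes the trial as greater than minimal risk. Staff cannot apply the sentence as it stands and must decide for themselves what was meant. A faithful translation would carry the problem to the sites in China. A monitor holding a site to the text could record nearly every enrolled patient as an eligibility deviation.

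**Working it through.** The plan gives no derived figure to reproduce. The check rests on definitions.

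**Inputs from the document (Section F1)**
- Prothrombin limit: "prothrombin time greater than 50% of control"
- Other two limits: "PTT greater than 50 sec, or INR greater than 2.0"

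**Input assumed**
- The International Sensitivity Index (ISI) of the laboratory reagent is not in the document. A range of 0.9 to 2.0 is used.

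**Formulas**
- Prothrombin ratio = patient's time / control time
- INR = ratio^ISI

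**Step 1: literal reading.** The exclusion applies when the ratio is above 0.5. A patient with normal clotting has a ratio of 1.0, and 1.0 > 0.5, so the patient is excluded. The same patient's INR is 1.0^ISI = 1.0 for every ISI, which is not above 2.0. Only a patient whose prothrombin time was half of control or less would pass. At that cut-off the INR is 0.5^0.9 = 0.54 to 0.5^2.0 = 0.25, so anyone with an INR above 2.0 has already been excluded by the prothrombin clause. The INR limit then does nothing.

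**Step 2: percentage read as prothrombin activity.** If normal activity is taken as about 100%, it is also above 50%, and normal patients are again excluded.

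**Step 3: percentage read as an increase over control.** The exclusion would apply when the ratio is above 1.5. These words are not in the text, but this reading makes the clause workable. The matching INR is:

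| Assumed ISI | INR at ratio 1.5 | Ratio at INR 2.0 |
|---|---|---|
| 0.9 | 1.44 | 2.16 |
| 1.0 | 1.50 | 2.00 |
| 1.2 | 1.63 | 1.78 |
| 1.4 | 1.76 | 1.64 |
| 1.7 | 1.99 | 1.50 |
| 2.0 | 2.25 | 1.41 |

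The two limits coincide at ISI = ln 2 / ln 1.5 = 0.693 / 0.405 = 1.71. Below that the prothrombin limit is the stricter; above it the INR limit is.

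**Step 4: where sites could differ.** Suppose one site uses the reading in step 3 and another disregards the prothrombin clause and relies on the INR. They differ on patients with a ratio above 1.5 and an INR not above 2.0. At ISI 1.0 that is an INR from 1.50 to 2.0; at ISI 1.2, from 1.63 to 2.0; at ISI 1.7, almost nobody; at ISI 2.0, nobody. The document gives no clotting values, so the number of such patients cannot be estimated.

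**The case against.** The strongest reply is that this is a wording slip that no clinician would follow. The population is routine outpatients, the same list excludes patients who cannot have endoscopy with biopsy, and the clause plainly aims at prolonged clotting. Section H3 also requires an initiation visit and investigator training before a collaborating site enrols. Most of this stands: literal application is improbable. It does not settle the point, because the intended rule is written nowhere and the description of the training does not mention this criterion.

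Four stronger readings are tempting, and the document does not support them.

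- *The line contradicts itself.* It does not. The limits are alternatives, and an exclusion that is not triggered does not thereby admit a patient.
- *On the increase-over-control reading, the mismatch between the two limits is itself an error.* Alternative exclusions need not coincide, and the stricter one governs. Nor is the prothrombin limit always the stricter: that holds only for an ISI below about 1.71.
- *The slip weakens protection against bleeding.* No reading of the prothrombin clause admits a patient with an INR above 2.0, because the INR limit excludes independently, as does the PTT limit. The literal reading excludes too many patients, not too few.
- *Every patient is biopsied, so every patient is exposed.* Section F2 requires biopsy of every Lugol-abnormal area. A patient without one has no biopsy under that rule.

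**Conclusion.** The point holds as a minor one. The prothrombin clause is wrong as written: it excludes essentially everyone with normal clotting and makes the INR limit redundant. That conclusion needs only the definition that a normal prothrombin time is about 100% of control.

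The practical consequence is smaller: possible variation between sites in the eligibility of patients with a mildly prolonged prothrombin time and an INR up to 2.0. Its extent depends on how each site reads the clause and on the local ISI, which is assumed here. Over an ISI of 0.9 to 2.0, a 50% increase over control matches an INR of about 1.44 to 2.25.

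A reader might infer that the trial cannot enrol, or that its power or estimates are compromised. The document supports neither. Sites are unlikely to apply the clause literally, and no sample size, power or analysis figure depends on it.

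**What to change.** The sponsor should reword the prothrombin clause so that it states what the percentage refers to and in which direction it excludes, and reconcile it with the INR limit so that one unambiguous criterion applies at all sites. It would help to say expressly that meeting any one limit excludes the patient. Which limit is right is a clinical decision, and none is proposed here.

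The cost is one line in the exclusion criteria, carried into the Chinese translation and the site submissions described in Section H3. Section G1 refers to the remaining patients to be accrued, so recruitment appears to be under way. The sponsor could also ask each site which reading it has been using, so that deviations are judged consistently.
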